3.3 Number of Subjects

Participants in this clinical investigation shall be referred to as “subjects.” It is anticipated that approximately 200 subjects will be enrolled into this study.

Please refer to [Section 10.2](#) for sample size considerations

3.4 Replacement of Subjects

Subjects who are withdrawn or removed from treatment or the study will not be replaced.

3.5 Estimated Study Duration

3.5.1 Study Duration for Participants

For an individual subject, the length of participation includes a 4-week screening period, up to a 36-month treatment period, an EOT visit, and an EOS visit. The maximum duration for a subject completing the study will be approximately 3 years and 2 months.

3.5.2 End of Study

Primary Completion: the time when the last subject is assessed or receives an intervention for the purposes of final collection of data for the primary analysis. This will occur once the last subject participating has completed the EOS visit.

4. SUBJECT ELIGIBILITY

Before any study-specific procedure is performed, the appropriate written informed consent must be obtained (see [Section 11.1](#)). In addition to written informed consent, the assent of the child also must be obtained if requested by the investigative site’s respective institutional review board/independent ethics committee (IRB/IEC).

Once informed consent (and assent, if applicable) has been obtained, the site will register the subject in the interactive voice response system (IVRS) and enter limited information about screening of potential candidate (sex, age, and race), date, and outcome of the screening process (eg, enrolled into study, reason for ineligibility, or refused to participate).

Investigators will be expected to maintain a screening log of all potential study candidates that includes limited information about the potential candidate (eg, date of screening).

4.1 Inclusion Criteria

- 4.1.1 Diagnosis of primary ITP according to The American Society of Hematology (ASH) Guidelines (Neunert et al, 2011) at least 6 months before screening, regardless of splenectomy status
- 4.1.2 Age \geq 1 year and $<$ 18 years at the time of providing informed consent
- 4.1.3 Subject must be refractory to a prior ITP therapy, having relapsed after at least 1 prior ITP therapy, or be ineligible for other ITP therapies
- Examples of prior therapy include but are not limited to: corticosteroids, IVIG, anti-D immunoglobulin, and platelet transfusions. Subjects who have failed a splenectomy are eligible for study participation
- 4.1.4 Subject has a documented platelet count \leq $30 \times 10^9/L$ or is experiencing bleeding that is uncontrolled with conventional therapies
- 4.1.5 Subject's legally acceptable representative (or subject, if applicable) has provided informed consent before any study-specific procedure; and subject has provided assent, where required by the IRB/IEC
- 4.1.6 Adequate hematologic, renal, and liver function during the screening period:
- Hemoglobin $>$ 10.0 g/dL
 - Serum creatinine \leq 1.5 times the upper limit of normal
 - Total serum bilirubin \leq 1.5 times the upper limit of normal
 - AST and ALT \leq 3.0 times the upper limit of normal

4.2 Exclusion Criteria

- 4.2.1 Known history of a bone marrow stem cell disorder (Any abnormal bone marrow findings other than those typical of ITP must be approved by Amgen before a subject may be enrolled in the study)
- 4.2.2 Prior bone marrow transplant or peripheral blood progenitor cell transplant
- 4.2.3 Known active or prior malignancy except non-melanoma skin cancers within the last 5 years
- 4.2.4 Known history of myelodysplastic syndrome
- 4.2.5 Known history of bleeding diathesis
- 4.2.6 Known history of congenital thrombocytopenia
- 4.2.7 Known history of hepatitis B, hepatitis C or human immunodeficiency virus
- 4.2.8 Known history of systemic lupus erythematosus, Evans syndrome, or autoimmune neutropenia
- 4.2.9 Known history of antiphospholipid antibody syndrome or known positive for lupus anticoagulant
- 4.2.10 Known history of disseminated intravascular coagulation, hemolytic uremic syndrome, or thrombotic thrombocytopenic purpura

Product: Romiplostim
Protocol Number: 20101221
Date: 15 August 2014

Page 24 of 69

- 4.2.11 History of venous thromboembolism or thrombotic events
- 4.2.12 Previous use of romiplostim. **Previous use of eltrombopag within 4 weeks of enrollment.**
- 4.2.13 Previous use of PEG-rHuMGDF, recombinant human thrombopoietin (rHuTPO) or any other platelet producing agent
- 4.2.14 Rituximab (for any indication) or 6-mercaptopurine within 8 weeks of enrollment, or anticipated use at any time during the study
- 4.2.15 Splenectomy within 4 weeks of the screening visit
- 4.2.16 Alkylating agents within 8 weeks before the screening visit or anticipated use during the time of the proposed study
- 4.2.17 Vaccinations known to decrease platelet counts within 8 weeks before the screening visit
- 4.2.18 Currently enrolled in another investigational device or drug study, or less than 30 days since ending another investigational device or drug study(s), or receiving other investigational agent(s)
- 4.2.19 Subject will have investigational procedures performed while enrolled in this clinical study
- 4.2.20 Female subject of child bearing potential (defined as having first menses) is not willing to use, in combination with her partner highly effective methods of birth control during treatment and for 1 month after the end of treatment
- 4.2.21 Subject is pregnant or breast feeding, or might become pregnant within 1 month after the end of treatment
- 4.2.22 Subject has known hypersensitivity to any recombinant Escherichia coli derived product (eg, Infergen[®], Neupogen[®], somatropin, and Actimmune[®])
- 4.2.23 Subject has previously enrolled into this study
- 4.2.24 Subject will not be available for protocol-required study visits or procedures, to the best of the subject's and investigator's knowledge
- 4.2.25 Subject has any kind of disorder that, in the opinion of the investigator, may compromise the ability of the subject to give written informed consent and/or to comply with all required study procedures

5. SUBJECT ENROLLMENT

Before subjects may be entered into the study, Amgen requires a copy of the site's written institutional review board/independent ethics committee (IRB/IEC) approval of the protocol, informed consent form and assent form if applicable. All subjects or legally acceptable representatives must personally sign and date the consent and assent form (if applicable) before study-specific procedures are performed. Adverse events are only reported for subjects enrolled in the study. Subjects are considered enrolled once they have been entered through the IVRS and have received their first dose of IP.

Product: Romiplostim
Protocol Number: 20101221
Date: 15 August 2014

Page 25 of 69

All subjects who enter into the screening period for the study (entry is defined as the point at which informed consent is signed) will receive a unique subject identification number before any study procedures are performed. This number will be used to identify the subject throughout the clinical study and must be used on all study documentation related to that subject.

The subject identification number must remain constant throughout the entire clinical study; it must not be changed at the time of rescreening or enrollment.

6. TREATMENT PROCEDURES

6.1 Classification of Product(s) and/or Medical Device(s)

The Amgen Investigational Product used in this study: romiplostim.

The Investigational Product Instruction Manual (IPIM), a document external to this protocol, contains detailed information regarding the storage, preparation, and administration of romiplostim.

6.2 Romiplostim

Romiplostim will be manufactured and packaged by Amgen Inc. and distributed using Amgen's clinical study IP distribution procedures. Romiplostim is supplied in a 5 mL single-use vial as a sterile, white, preservative-free, lyophilized powder containing a protein concentration of 0.5 mg/mL of 10 mM histidine, 4.0% mannitol, 2.0% sucrose, 0.004% polysorbate 20, and a pH 5.0 when reconstituted with 1.2 mL of sterile water for injection.

6.2.1 Dosage, Administration, and Schedule

IP will be administered as a subcutaneous injection. The starting dose of romiplostim will be 1 µg/kg based on the subject's recorded screening weight. Initially, IP will be administered in the clinic by a qualified health care provider and subjects will return to the clinic weekly to provide blood samples for platelet counts and undergo any dose titrations under the supervision of the treating physician. Subjects who receive their first 8 doses in the clinic and achieve a stable dose of romiplostim for at least 4 weeks may be allowed to self-inject romiplostim or have the injection administered by a caregiver. Weekly dose increases will continue in increments of 1 µg/kg up to a maximum dose of 10 µg/kg in an attempt to reach a target platelet count of $\geq 50 \times 10^9/L$. Dose adjustments will be allowed to maintain a platelet count between $\geq 50 \times 10^9/L$ and $\leq 200 \times 10^9/L$. Dose adjustments will be evaluated every 12 weeks due to potential body weight changes.

Product: Romiplostim
Protocol Number: 20101221
Date: 15 August 2014

Page 26 of 69

If a dose of < 0.05 mL is required, dilution of romiplostim in a 1:2 ratio (a protein concentration of 0.25 mg/mL) or a 1:4 ratio (a protein concentration of 0.125 mg/mL) may be made with 0.9% saline to ensure an appropriate dispensable volume is delivered.

Subjects will be monitored for the onset of a sustained platelet response (see [Section 3.1.1](#)) and, if achieved, may dose-reduce romiplostim. If a subject no longer requires treatment with romiplostim but there is subsequently a fall in platelet counts of < 50 x 10⁹/L during the 36-month treatment period, treatment with romiplostim should resume at the initial weekly dose of 1 µg/kg.

The effects of overdose of romiplostim are not known. In high-dose preclinical studies, the noted effects were related to the pharmacological action of romiplostim. In the event of an overdose, platelet counts should be monitored frequently. Please refer to [Section 6.2.2](#) for dosage adjustments.

Specific romiplostim details, including labeling, storage, preparation, dilution, administration, etc., are provided in a separate Investigational Product Instruction Manual. Each romiplostim box number is to be recorded on each subject's Investigational Product Administration electronic case report form (eCRF).

6.2.2 Dosage Adjustments: Delays or Rules for Withholding Investigational Product

Each subject's dose will be adjusted based on platelet counts. The rules outlined in [Table 1](#) describe how the adjustments are to be made during the study.

Table 1. Dose Adjustment Rules

Platelet count (x 10 ⁹ /L)	Investigational Product Dose Adjustment Rule ^a
< 50 ^b	Increase dose by 1 µg/kg each week (to a maximum of 10 µg/kg)
50 to 200 ^b	Dose remains constant
> 200 to < 400 ^{b,c}	After the platelet count remains in this range for 2 consecutive weeks, dose reduce by 1 µg/kg
≥ 400 ^{b,c,d}	Withhold the dose and dose reduce by 1 µg/kg on the next scheduled day of dosing when platelet count falls < 200 x 10 ⁹ /L

^a If the platelet count is elevated in response to the initiation or increase in dose of another ITP medication, then the same dose of IP should be administered when the platelet count is ≤ 200 x 10⁹/L.

^b Romiplostim may be used with other therapies for ITP (refer to Section 6.4). If the subject's platelet count is ≥ 50 x 10⁹/L, other ITP therapies may be reduced or discontinued.

^c If the current dose is 1 µg/kg and a dose reduction is required, the dose will be withheld until the platelet count falls to < 50 x 10⁹/L. Once the platelet count is < 50 x 10⁹/L, dosing will resume at a dose of 1 µg/kg using the dose adjustment rules above.

^d If platelet count ≥ 400 x 10⁹/L is due to rescue medications, it is at the discretion of the investigator to reduce the dose by 1 µg/kg.

In situations in which withholding a romiplostim dose results in a rapid drop in platelet count, an alternate dosing schedule may be authorized on a case-by-case basis with the approval of an Amgen medical monitor.

The subject's body weight will be reassessed every 12 weeks. Subsequent doses of romiplostim will be re-calculated using the new weight. If the volume (mL or µL) of IP will be increasing due to an increase in body weight > 2.5 kg, the unit dose (µg/kg) of IP should not be increased until a platelet count has decreased to < 50 x 10⁹/L requiring an increase in dose.

All doses of romiplostim will be administered on a weekly basis. Should a subject miss a dose of romiplostim, the dose can be taken within 1 day of the scheduled date of administration. Should the subject miss a dose outside of the 1 day window, the subject will continue with the subsequent dose at the next scheduled weekly date.

Dosing will be stopped at any time during the study if neutralizing antibodies to romiplostim or to eTPO are detected.

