6.4 Concomitant Therapy

Throughout the study, investigators may prescribe any concomitant medications or treatments deemed necessary to provide adequate supportive care, except for those listed in [Section 6.6](#).

All prescription and non-prescription concomitant medications, used to treat conditions other than ITP, administered at the time of enrollment, ongoing after enrollment, as well as changes in such concomitant medications and any new concomitant medications taken while the subject is on study, will be recorded on the appropriate eCRF through the EOT or the EOS visit, whichever is later.

Concomitant and Rescue Therapy for ITP

Concomitant medications are allowed for subjects enrolled into the study in any situation deemed medically necessary to increase platelet counts. Medications to increase platelet counts starting before enrollment and continuing unchanged (dose and schedule) while on treatment with romiplostim will be defined as concomitant medications for ITP. Rescue medication is defined as any medication or transfusion, other than romiplostim and excluded medications, that is administered after enrollment to the subject with the intent of raising platelet counts or to prevent bleeding and includes concomitant medications for ITP in which the dose and/or schedule is increased. For the purposes of this study, the permitted rescue medications include the following:

- corticosteroids
- platelet transfusions
- IVIG
- azathioprine
- anti-D immunoglobulin
- danazol

Antifibrinolytics can be used at any time during the study and will not be considered rescue medication(s).

Inhaled and/or topical corticosteroids intended to treat non ITP conditions (eg, inhaled steroids for asthma) will not be considered concomitant medications for ITP or rescue

Product: Romiplostim
Protocol Number: 20101221
Date: 15 August 2014

Page 30 of 69

medications and continuing on such medication(s) will not affect the definition of platelet response.

Rescue medication is allowed throughout the duration of the study when platelet counts are $< 20 \times 10^9/L$ and/or when a subject has bleeding or wet purpura. Rescue medication is also allowed in any situation deemed medically necessary by the treating physician to increase platelet counts to treat or prevent bleeding.

Reduction or discontinuation of concomitant or rescue medications for ITP is recommended based on investigator judgment when platelet counts are $\geq 50 \times 10^9/L$.

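### Table 1 of the protocol gives opposite next doses (reduce or increase) for a child on 2 to 10 µg/kg who was held for a count ≥400 and returns below 50

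*Protocol*

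**What the plan says.** Protocol Section 6.2.2 makes Table 1 the rule set for adjusting romiplostim by platelet count (all counts here are × 10⁹/L).

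- **Row ≥400:** the dose is withheld and then lowered by 1 µg/kg "on the next scheduled day of dosing when platelet count falls" below 200.
- **Row <50:** "Increase dose by 1 µg/kg each week (to a maximum of 10 µg/kg").
- **Footnote a**, attached to the heading of the rule column: if the count rose because another ITP medication was started or increased, "then the same dose of IP should be administered when the platelet count is" at or below 200.
- **Footnote c**, attached to the >200 to <400 and ≥400 rows: a child already at 1 µg/kg who needs a reduction is held until the count is below 50 and then restarts at 1 µg/kg.
- **Footnote d**, attached to the ≥400 row: if the count is due to rescue medication, "it is at the discretion of the investigator to reduce the dose by 1" µg/kg.

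Below the table, the protocol foresees that withholding a dose may cause a rapid fall in the count. In that event "an alternate dosing schedule may be authorized on a case-by-case basis with the approval of an Amgen medical monitor".

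Protocol Section 6.4 defines rescue as medication or transfusion given after enrollment to raise platelets or prevent bleeding, and adds that it "includes concomitant medications for ITP in which the dose and/or schedule is increased".

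The replacement table in Amendment 2 has the same wording in these rows and footnotes, so this is current text. The SAP contains no dosing rule.

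**The concern.** A count below 50 is also below 200. A child who was held at ≥400 and comes back below 50 therefore satisfies two rows at once, and one lowers the dose while the other raises it. Nothing in the section says which row governs the first dose after a hold.

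About 50 centers (Protocol Section 3.2) make these decisions week by week. The child concerned has just swung from a very high count to a low one, so the consequence is first a matter of safety. There is also a statistical side. The primary endpoint is time at ≥50, and differences between sites in how the table is read would feed into dose and platelet count without reflecting the drug. Two sites could take opposite actions and both claim to have followed the protocol.

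The second, lesser question is what happens when the count ≥400 was caused by rescue. Footnote a says the dose should stay the same; footnote d allows it to be reduced.

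**Working it through.** The plan gives no figure to reproduce. The check applies the written rules literally to each dose.

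**Inputs.** Let d be the dose before the hold, in whole µg/kg from 1 to 10 (start at 1, steps of 1, maximum 10: Protocol Sections 6.2.1 and 6.2.2).

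**Case 1: held for ≥400, not caused by another ITP treatment, and count <50 at the next dosing day.**

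- ≥400 row: next dose = d − 1
- <50 row: next dose = the smaller of d + 1 and 10
- At d = 1, footnote c applies and gives 1, so there is no conflict.

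| d before hold | ≥400 row | <50 row | Gap |
|---|---|---|---|
| 1 | 1 (footnote c) | 1 (footnote c) | 0 |
| 2 | 2 − 1 = 1 | 2 + 1 = 3 | 2 |
| 5 | 5 − 1 = 4 | 5 + 1 = 6 | 2 |
| 9 | 9 − 1 = 8 | 9 + 1 = 10 | 2 |
| 10 | 10 − 1 = 9 | 10 (maximum) | 1 |

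For d from 2 to 9 the gap is (d + 1) − (d − 1) = 2 µg/kg. At d = 10 it is 10 − 9 = 1 µg/kg. In relative terms it is widest at d = 2 (3/1 = three-fold) and narrowest at d = 10 (10/9 = 1.11).

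The rapid-drop sentence does not close the gap. It is permissive, it needs approval case by case, it concerns the schedule, and it gives no dose to use if no approval is sought.

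**Case 2: count ≥400 caused by rescue.** An ITP medication newly started or increased after enrollment is rescue under Section 6.4 and is also the trigger of footnote a, so such a child falls under both footnotes.

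- Footnote a: next dose = d
- Footnote d: next dose = d or d − 1, as the investigator decides

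For d from 2 to 10 the two differ by 1 µg/kg if the discretion is used, and by nothing if it is not. At d = 5 this is 5 against 5 or 4.

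**Threshold.** The ≥400 row resumes at <200, footnote a at ≤200. They disagree only at a count of exactly 200.

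**The case against.** The best reply is that the ≥400 row is a two-step instruction carried forward until it is completed. It has to work that way to have any effect: on a return at 50 to <200 it must already override the 50-to-200 row, which holds the dose constant. Read so, it would also cover a return below 50, and the rapid-drop sentence would send difficult cases to the medical monitor. This reading is reasonable, but it is not written. The <50 row has no exception after a hold. Footnote c shows that the authors wrote an explicit rule for a return below 50 at 1 µg/kg and none for higher doses.

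On the footnotes, the reply is stronger. Footnote d is attached only to the ≥400 row and can be read as the specific exception to footnote a. Discretion to reduce includes not reducing, so giving the same dose satisfies both. The overlap is also not complete, since rescue includes transfusion and footnote a speaks of medication. What stands is a missing statement of which footnote governs.

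A reader might also infer three things that the documents do not support:

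- **A conflict at 201 to 399 for a held child.** The ≥400 row keeps the hold until the count is below 200. The >200 to <400 row only says to reduce after two consecutive weeks in range; it does not tell a site to end a hold.
- **A frequency from the earlier pediatric study.** Protocol Section 2.4 reports rescue in 2 of 17 romiplostim subjects (11.8%). That is any rescue use. It is neither the rate of rescue-driven counts ≥400 nor the rate of returns below 50 after a hold.
- **That adherence to the dose rules cannot be monitored.** Counts used for dosing go on the eCRF (Protocol Section 7.1.2), and doses given are listed (Protocol Section 10.3.4.3, SAP Section 10.6.5), so these weeks can be found. What the text leaves open is which action counts as compliant.

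**Conclusion.** The main point holds on the current text. For a child on 2 to 10 µg/kg who returns below 50 after a hold at ≥400, Table 1 contains two opposite instructions and no order of precedence. They differ by 2 µg/kg at doses of 2 to 9 and by 1 µg/kg at 10. The overlap of footnotes a and d (at most 1 µg/kg, and only if discretion is used) and the mismatch at exactly 200 are minor clarifications.

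This is a gap at one decision point and does not show that the table fails in general. The result assumes a literal reading and that no document outside this protocol and SAP settles the order. How often either case arises is not stated, so the effect on time in response cannot be sized. The trial is single-arm and descriptive, and counts within 4 weeks of rescue are already treated as non-response (Protocol Section 10.3.2.1), which limits what the footnote question can do to the primary endpoint. That rule does not limit the main conflict when the hold had nothing to do with rescue. The point is worth correcting because it bears on safety and the correction is cheap.

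**What to change.** The sponsor's clinicians should reconcile the ≥400 row, the <50 row and footnotes a, c and d, so that each combination of count and history leads to one instruction. The revised text should state:

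1. which row governs the first dose after a ≥400 hold when the count is below 50 and the dose is above 1 µg/kg;
2. which of footnotes a and d governs a count ≥400 caused by rescue;
3. one resume threshold, used throughout.

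The choice of rule belongs to the sponsor's clinicians, and none is suggested here. The cost is a few lines of table and footnote wording in an amendment, plus a notice to sites. Amendment 2 already corrected this same table, so the route is established. No new data collection is needed.

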6.2.3 Non-responders to Romiplostim

Subjects with a platelet count of < 20 x 10⁹/L for 4 consecutive weeks at the maximum romiplostim dose of 10 µg/kg should be discontinued from romiplostim and will be considered non-responders. Non-responders will be discontinued from the study and undergo all EOT and EOS procedures.

If the subject is a non-responder but the investigator believes the subject has obtained clinical benefit, the investigator must contact the Amgen medical monitor for

Product: Romiplostim
Protocol Number: 20101221
Date: 15 August 2014

Page 28 of 69

consideration of continued participation in the study. If subject is allowed to remain on study and receive a stable romiplostim dose for at least 4 weeks, the subject will be eligible for self- administration.

